4.3.2.1 Live or Attenuated Vaccinations

Immunization with a live or attenuated vaccine is prohibited for the duration of study participation, including the 8-week follow-up period after the administration of the last dose. See Section 5.1.1.1 for further details and precautions around vaccinations.

4.3.2.2 CYP3A Inhibition

In vitro studies suggest that GDC-0853 is a time-dependent inhibitor of CYP3A with inhibitory constant (K_i) values of approximately 10 μ M (Study 13-0384). Although peak plasma concentrations are anticipated to be much lower than 10 μ M (preliminary results from Study GA29347 indicate that a BID dose of 250 mg powder in capsule resulted in a mean steady-state C_{max} of approximately 849 nM), it is possible that GDC-0853 inhibition of CYP3A may alter the metabolism of CYP3A substrates, including estrogen derivatives such as ethinylestradiol, subsequently leading to an increase in plasma concentrations of these drugs (see below and the GDC-0853 Investigator's Brochure). Medications that are sensitive substrates of CYP3A or substrates of CYP3A with a narrow therapeutic window should be used with caution during this study (refer to Appendix 3 for a list of relevant medications).

Ethinylestradiol is metabolized by CYP3A; therefore, plasma concentrations may increase in the presence of GDC-0853. The use of hormone-replacement therapy containing ethinylestradiol or hormonal contraceptives containing ethinylestradiol, with the concomitant use of a barrier method, is permitted during this study (see Appendix 4); however, these agents should be used with caution and patients should be counseled regarding the potential risks and benefit of these medications per the local prescribing information. Any increase in ethinylestradiol plasma concentrations is anticipated to be modest at most because CYP-mediated oxidation appears to be a relatively minor component of orally administered ethinylestradiol (Zhang et al. 2007). Although contraceptive efficacy is not expected to be impacted, increased ethinylestradiol plasma concentrations may lead to an increase in common side effects, such as nausea, breast tenderness, and headaches, and to a theoretical increase in rare dose-related events such as thromboembolism (Inman et al. 1970).

In vitro data suggest that GDC-0853 is metabolized by CYP3A, and there is a moderate to high potential for a drug-drug interaction with any medication that strongly inhibits or induces this enzyme. Therefore, medications in the following categories (listed in detail in Appendix 3) should be avoided for 7 days or 5 half-lives, whichever is longer, prior to the first dose of study drug until the last dose of study drug. If use of one of these medications is necessary, the risks and benefits should be discussed with the Medical Monitor prior to concomitant administration with study drug.

- Moderate or strong CYP3A inhibitors
- Moderate or strong CYP3A inducers

Data also suggest that GDC-0853 inhibits CYP3A, and there is a moderate to high potential for a drug-drug interaction with any medication that is metabolized by CYP3A. Plasma concentrations of the medications in the following categories (listed in detail in Appendix 3) may increase; therefore, they should be used with caution:

- Sensitive CYP3A substrates
- CYP3A substrates with a narrow therapeutic index

The medications listed above and in Appendix 3 are not necessarily comprehensive. Thus, the investigator should consult the prescribing information for any concomitant medication as well as the Internet references provided below when determining whether a certain medication is metabolized by or strongly inhibits or induces CYP3A. The investigator should contact the Medical Monitor if questions arise regarding medications not listed above.

http://www.fda.gov/downloads/Drugs/GuidanceComplianceRegulatoryInformation/Guidances/UCM292362.pdf

http://medicine.iupui.edu/clinpharm/ddis/table.aspx

4.3.3 Prohibited Food

Use of the following foods is prohibited during the study and for at least 7 days prior to initiation of study treatment: furanocoumarin derivatives as found in grapefruit, Seville orange, pomegranate, or star fruit juice or products.

4.4 STUDY ASSESSMENTS

Please see Appendix 1 for the schedule of assessments to be performed during this study.

The following results, collected at the final Day 84 study visit in the blinded Study GA29350, will be used as baseline assessments in Study GA30067:

- Pregnancy test, ECGs, vital signs, physical examination
- Joint counts, Patient Global Assessment of Disease Activity, Patient Assessment of Arthritis Pain, Physician's Global Assessment of Arthritis
- HAQ-DI, FACIT-Fatigue Scale, SF-36v2

- Laboratory tests
- Concomitant medications
- PK/PD assessments

4.4.1 Informed Consent Forms and Screening Log

Patients will be screened on Day 84 of the blinded Study GA29350 to confirm that they meet the entrance criteria for this study. The study investigator or subinvestigator will discuss with each patient the nature of the study, its requirements, and its restrictions.

Written informed consent for participation in this study must be obtained before performing any study-related procedures.

Informed Consent Forms for enrolled patients and for patients who are not subsequently enrolled will be maintained at the study site.

Patients *must* meet all eligibility criteria before *receiving their* first *open-label* dose in this study. The investigator will maintain a screening log to record details of all patients screened and to confirm eligibility or record reasons for screening failure, as applicable.

4.4.2 Medical History and Demographic Data

Any adverse events that commenced during and are still ongoing at the end of the blinded Study GA29350 will be recorded as "unresolved" and reopened in Study GA30067 with the start date, adverse event term, and initial intensity of the adverse event being identical to those in the Study GA29350. Adverse events that occurred during the core study and resolved before the patient's enrollment into Study GA30067 will be reported in the patient's medical history according to their medical relevance.

4.4.3 **Physical Examinations**

A complete physical examination should be performed at Day 1 (which is Day 84 of Study GA29350) and should include an evaluation of the head, eyes, ears, nose, and throat and the cardiovascular, dermatological, musculoskeletal, respiratory, GI, genitourinary, and neurological systems. Any abnormality identified at baseline should be recorded on the General Medical History and Baseline Conditions eCRF.

At subsequent visits or as clinically indicated, limited, symptom-directed physical examinations should be performed. Changes from baseline abnormalities should be recorded in the patient notes. New or worsened clinically significant abnormalities should be recorded as adverse events on the Adverse Event eCRF.

4.4.4 Vital Signs

Vital signs will include measurements of pulse rate, systolic and diastolic blood pressures while the patient is in a seated position for at least 5 minutes, and temperature.

4.4.5 Efficacy Assessments

Questionnaires will be self-administered before the patient receives any information on disease status, prior to the performance of non-PRO assessments and prior to the administration of study treatment. In cases where this is logistically challenging, potentially painful procedures will be performed no less than 15 minutes prior to initiation of the PRO measures.

The sequence of assessments where efficacy is assessed (see Appendix 1 for Schedule of Assessments) will be standardized as follows:

Patient-Reported Outcome Measures:

```
Patient's Assessment of Arthritis Pain (see Section 4.4.6.1)
```

Patient's Global Assessment of Arthritis (see Section 4.4.6.2)

```
HAQ-DI (see Appendix 5)
```

SF-36v2 (see Appendix 6)

FACIT-Fatigue Scale (see Appendix 7)

- Laboratory samples for safety, efficacy, biomarkers, and pharmacokinetics should be drawn after patient self-assessments are completed
- Investigators

Joint counts

Physician's Global Assessment of Arthritis Visual Analog Scale (VAS), safety assessments (adverse events, vital signs, concomitant medications, review of laboratory data)

• Administration of GDC-0853 in clinic (only at the indicated visits, per Appendix 1)

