1.3 STUDY RATIONALE AND BENEFIT-RISK ASSESSMENT

The results from the Phase I studies, nonclinical toxicology studies, and studies in nonclinical models of RA support further evaluation of GDC-0853 as a potential treatment for RA. The goal of this Phase II, open-label extension (OLE) Study GA30067 is to evaluate the long-term safety and efficacy of GDC-0853 in combination with methotrexate (MTX) and/or other disease-modifying anti-rheumatic drugs (DMARDs) in patients with active RA. Participation in Study GA30067 is optional and is based on the patient's preference, the investigator's clinical judgment, and meeting the eligibility requirements for this protocol. Eligible patients will have participated in Study GA29350, which comprises of 2 cohorts. In Cohort 1, three doses of GDC-0853 will be compared with placebo and HUMIRA® (adalimumab) in patients with an inadequate response to

MTX). In Cohort 2, one dose of GDC-0853 will be compared with placebo in patients with an inadequate response to TNF inhibitors). Study GA30067 is designed with safeguards in place to optimize clinical efficacy and minimize safety risks. Patients who do not derive clinical benefit from GDC-0853, based on at least a 20% improvement in both SJCs and TJCs, relative to baseline values in the blinded Study GA29350, should not continue in the study past Week 24 of Study GA30067. In addition, safety in both the blinded Study GA29350 and the open-label Study GA30067 will be monitored at regular intervals by the Internal Monitoring Committee (IMC). If there are any concerning safety issues that arise, either as specified in Section 5.1.2 or based on the investigator's judgment and discussion with the Medical Monitor, dose reductions and dose interruptions will be allowed in Study GA30067. The blinded Study GA29350 is designed with an interim analysis at approximately 150 patients (i.e., 30 patients per arm), at which point the IMC will evaluate the unblinded efficacy and safety. If the benefit-risk assessment is not deemed to be favorable, based on safety concerns and/or suboptimal efficacy, then a futility decision will be triggered to minimize patients' exposure to GDC-0853.

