2. OBJECTIVES AND ENDPOINTS

This OLE study will evaluate the long-term safety and efficacy of GDC-0853 in patients with RA. Specific objectives and corresponding endpoints and analyses for the study are outlined in Table 1.

Table 1 Primary (Safety), Efficacy, Pharmacokinetic, and Exploratory Objectives with Corresponding Endpoints

Objectives	Corresponding Endpoint(s)	
Primary Objective (Safety)		
To evaluate the long-term safety of GDC-0853 over an extended treatment period of up to 52 weeks	 The nature, frequency, severity, and timing of adverse events Changes in vital signs, physical findings, ECGs, and clinical laboratory results during and following GDC-0853 administration 	
Primary Efficacy Objective		
 To evaluate the efficacy of GDC-0853 (analyzed separately for MTX-IR and TNF-IR patients) at Week 52 relative to baseline in Study GA29350 	ACR50 response at Week 52	
Secondary Efficacy Objective		
 To determine the improvement in disease activity through 52 weeks of treatment (analyzed separately for MTX-IR and TNF-IR patients) relative to baseline in Study GA29350 	 ACR50 response up to Week 12 ACR20, ACR70, DAS 28-3 (CRP), DAS 28-4 (CRP), DAS 28-3 (ESR), and DAS 28-4 (ESR) response up to Week 52 	
• To assess DAS28 remission (<2.6) and LDA (<3.2) state	States up to Week 52	
• To assess ACR/EULAR remission according to the Boolean-based definition (tender joint count ≤1, swollen joint count ≤1, CRP ≤1, and patient global assessment ≤1)	Remission status up to Week 52	
• To assess SDAI-based remission (defined as ≤3.3 for ACR/EULAR remission) and CDAI-based remission	Remission status up to Week 52	
To assess efficacy based on the individual components of the ACR relative to baseline in Study GA29350	Response status up to Week 52 for: Tender/Painful Joint Count (68) Swollen Joint Count (66) Patient's Assessment of Arthritis Pain Patient's Global Assessment of Arthritis Physician's Global Assessment of Arthritis CRP HAQ-DI	

Objectives	Corresponding Endpoint(s)	
To evaluate the effect of GDC-0853 on health-related quality of life	SF-36, standard, Version 2, questionnaire through 52 weeks	
To evaluate the effect of GDC-0853 on fatigue	FACIT-Fatigue Scale up to Week 52	
Pharmacokinetic Objectives		
To characterize the pharmacokinetics of GDC-0853 in patients using a population PK approach	Steady-state PK parameters (AUC _{0-t} , C _{trough} , t _{1/2} , apparent CL/F)	
Exploratory Pharmacokinetic Objectives:		

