3.1 DESCRIPTION OF THE STUDY

This is a Phase II, multicenter, OLE study to evaluate the long-term safety and efficacy of GDC-0853 in patients with RA who have completed 12 weeks of study treatment in Study GA29350. The population for this study consists of patients with RA who have had an inadequate response to previous MTX therapy (Cohort 1 of Study GA29350) or previous TNF and MTX therapy (Cohort 2 of Study GA29350).

This OLE study will be conducted in centers that have participated in the double-blind, Phase II Study GA29350. The maximum number of patients potentially enrolling in this study will be approximately 580 patients. Patients will be assigned the same patient number they had in Study GA29350.

Eligible patients from Study GA29350 who elect to participate will receive treatment with GDC-0853 at 200 mg BID in an open-label fashion for 52 weeks, followed by a safety follow-up period of 8 weeks. Dose reductions of GDC-0853 to 200 mg QD are allowed for specific safety reasons (see Section 5.1.2) and may be allowed on the basis of clinical safety concerns of the investigator, only after discussion with the Medical Monitor. Eligible patients will be enrolled directly into Study GA30067 following treatment completion at Week 12 of Study GA29350 (e.g., they will not undergo the 8 weeks of safety follow-up in Study GA29350). The dose and route of administration of MTX at the end of the blinded Study GA29350 should be continued and held stable for the first 12 weeks of the OLE study. Discontinuation of MTX or alteration of the MTX dose prior to Week 12 is discouraged. Use of additional DMARDs other than MTX is discouraged prior to Week 12.

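### The only stated baseline for laboratory, ECG, vital-sign and PK/PD values is parent Day 84, which is on GDC-0853 for some patients and before GDC-0853 for the rest

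*Combined protocol and SAP*

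**What the plan says.** Section 4.4 lists pregnancy test, ECGs, vital signs, physical examination, joint counts, questionnaires, laboratory tests and PK/PD assessments as results which, "collected at the final Day 84 study visit in the blinded Study GA29350, will be used as baseline assessments in Study GA30067". Footnote g of Appendix 1 repeats the rule.

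Patients roll over directly: "they will not undergo the 8 weeks of safety follow-up in Study GA29350" (Section 3.1). Section 1.3 describes where they come from: "In Cohort 1, three doses of GDC-0853 will be compared with placebo and" adalimumab, and "In Cohort 2, one dose of GDC-0853 will be compared with placebo in patients with" an inadequate response to TNF inhibitors.

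Table 1 refers ACR response and disease activity to the parent-study baseline. The primary safety objective has as one of its endpoints "Changes in vital signs, physical findings, ECGs, and clinical laboratory results during and following GDC-0853 administration", with no reference value. Section 6.4 names none either and separates results only by parent *treatment cohorts*. Section 6.7 scales biomarkers to baseline and tests whether baseline biomarkers pick out patients with greater benefit, without defining baseline or predose. Section 4.4.2 has adverse events still ongoing at the end of the parent study reopened in the OLE with their parent start dates; 6.4 does not say how they are counted.

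**The concern.** Safety is the primary objective, and changes in laboratory values, ECGs and vital signs are part of its endpoint. With a single Day 84 reference, change from baseline means change since first GDC-0853 exposure in one group of patients and change after about 12 weeks of exposure in the other.

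The same applies to biomarkers. Section 3.3.3 speaks of assessments before and after treatment, and the note to Table 2 separates baseline from time points during treatment. In the GDC-0853 arms, Day 84 is a time point during treatment. Phosphorylated BTK, listed in Table 2, is the plainest example: scaled to an on-drug value, it cannot show inhibition that was already present.

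For the predictor analysis, ACR response is counted from the parent baseline, so a Day 84 biomarker is taken partway through the response window, after drug in some patients only.

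**Working it through.** The documents give no figure to reproduce for this point, so the check is of the text, the arms and the schedule.

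**1. Reference value by data type**

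| Data | Reference stated | Where |
|---|---|---|
| ACR and disease activity | Parent-study baseline | Table 1 |
| Week 12 and Week 24 joint-count rules | Parent-study baseline | Sections 3.1, 3.3.5.1, 4.5.2 |
| Pre-existing conditions | Parent screening | Section 5.3.5.8 |
| Laboratory, ECG, vital signs, PK/PD | Parent Day 84 | Section 4.4; Appendix 1, footnote g |
| Safety changes; 6.4; 6.7 | None | Table 1; 6.4; 6.7 |

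For safety and PD values, Day 84 is therefore the only baseline stated.

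**2. Who is on drug at Day 84**

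Cohort 1 has 3 GDC-0853 arms + placebo + adalimumab = 5 arms. This agrees with the parent "interim analysis at approximately 150 patients (i.e., 30 patients per arm": 150/30 = 5. Three of the five arms are on GDC-0853; at 30 per arm that is 90/150 = 60%. Only placebo, 30/150 = 20%, is on neither GDC-0853 nor adalimumab. Cohort 2 has 1 GDC-0853 arm of 2, which is 50% if allocation is 1:1 (assumed).

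If all of the roughly 580 patients entered and allocation were equal within each cohort (assumed), the number with an on-drug baseline would lie between 580 × 0.5 = 290 and 580 × 0.6 = 348, depending on the cohort split.

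Section 4.2.2.1 and footnote m of Appendix 1 disagree on when the last parent dose is taken (the morning of Day 84, or the evening before) and must be reconciled. Under either, Day 84 follows about 12 weeks of treatment.

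**3. What the Day 84 reference removes**

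Let V(pre) be the last value before the first GDC-0853 dose, V(84) the Day 84 value and V(t) an OLE value.

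- Former GDC-0853 arms: V(t) − V(84) = [V(t) − V(pre)] − [V(84) − V(pre)]. The last bracket is the change that arose in the parent study, and it drops out. On a ratio scale, V(t)/V(84) = [V(t)/V(pre)] ÷ [V(84)/V(pre)].
- Former placebo and adalimumab arms: V(84) = V(pre), so nothing drops out, although the adalimumab patients' value is on adalimumab.

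The documents give no value for V(84) − V(pre), so its size cannot be calculated.

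**4. Whether the OLE schedule supplies a drug-free value**

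For former GDC-0853 arms, weeks since first dose = OLE week + 12 (the parent dose may differ from the OLE dose).

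| Measure | OLE weeks | Weeks since first GDC-0853 dose | 8-week follow-up |
|---|---|---|---|
| Quantitative Ig | 0, 12, 24, 36, 52 | 12, 24, 36, 48, 64 | No |
| T, B and NK cells | 0, 12, 24, 52 | 12, 24, 36, 64 | Yes |
| Serum, plasma and RNA biomarkers | 0, 12, 52 | 12, 24, 64 | Yes |

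No scheduled OLE sample in these patients is pre-drug. Immunoglobulins have no scheduled off-drug sample either; the others have one, after treatment ends.

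**The case against.** The strongest reply is that Section 4.4 is a visit-sharing rule. Its list includes joint counts and HAQ-DI, yet Table 1 refers those to the parent baseline, so the list does not by itself fix the analysis reference; and 6.4 specifies no change-from-baseline table. This stands in part: how far the safety displays are affected depends on tables not described. But for safety and PD values nothing overrides the list, and 6.7 does call for scaling to baseline.

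Second, *treatment cohorts* may mean parent arms. Table 1 names the two populations as MTX-IR and TNF-IR when it means them, and listing by dose in 6.7 could mean parent dose. On that reading the two kinds of baseline are not mixed within a safety display. A reader might infer that they will certainly be pooled; the documents do not support that. Nor do they exclude it, since Section 3.1 uses the word for populations, as in "previous MTX therapy (Cohort 1 of Study GA29350". Display by arm would still leave an on-drug baseline in the GDC-0853 arms.

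Third, the first 12 weeks are observed in the blinded parent trial, OLE entry is a defensible reference for an extended treatment period, no tests are planned, and the biomarker work is exploratory. All of this stands and limits the importance of the point. It supports keeping the Day 1 reference, but not as the only one.

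Fourth, a Data Analysis Plan may define baseline. Section 6.5 cites it for efficacy; 6.4 and 6.7 do not refer to it, and it is not among the documents.

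**Conclusion.** The point holds as a defect in the stated reference value, and it should be fixed before the analyses are specified. Followed as written, baseline-scaled biomarkers and any change-from-baseline safety summary omit change that arose during the parent study in 3 of 5 Cohort 1 arms and 1 of 2 Cohort 2 arms, and the predictor analysis combines on-drug and pre-drug values. The patient shares of 60% and 50% rest on interim arm sizes and on assumed 1:1 allocation respectively.

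A reader might infer that a known drug effect, or a safety signal, will be hidden. The documents do not support that. The nearest indication is the fall in dog B-cell counts from 2.1 µM·h (Section 1.3), against a mean exposure expected to be below 10 µM·h (Section 3.3.1). That effect is not timed, and actual exposure is not shown to reach 2.1. Nor is the safety assessment as a whole undermined: absolute levels and readings based on grade or upper limit of normal do not depend on the baseline.

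**What to change.** In 6.4 and 6.7, present change from the last value before the first GDC-0853 dose in either study alongside change from OLE Day 1. That value is the parent pre-treatment value for former GDC-0853 arms and Day 84 for former placebo and adalimumab arms. State that *treatment cohorts* means parent-study treatment arm within Cohorts 1 and 2.

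For the predictor analysis, use the parent pre-treatment biomarker in former GDC-0853 arms, where it matches the baseline used for ACR response. Analyse former placebo and adalimumab patients separately: their last pre-GDC-0853 value is taken about 12 weeks after the baseline from which their ACR response is counted.

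List reopened parent adverse events separately from events with onset in the OLE, using the retained start dates. Section 4.4 can remain as the visit-sharing rule.

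The cost is a merge with parent data and extra tables, with no new visits or samples. The link exists ("Patients will be assigned the same patient number they had in Study GA29350", Section 3.1), Section 1.3 says that immunoglobulins are measured in both studies, and efficacy already needs parent baseline data. The parent protocol is not among the documents, so a pre-treatment sample for each biomarker must be confirmed, and the Data Analysis Plan should be checked first.
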